6.7.3 Laboratory Values

Laboratory results will be summarized using Système International (SI) units, as appropriate.

On-treatment laboratory tests will be defined as laboratory tests conducted from the start of treatment to no more than 30 days after the last dose of study treatment. Central laboratory test results will be primary data source for laboratory analyses. Only when the central laboratory tests results are missing, the local laboratory test results will be used as substitute.

For all quantitative parameters listed in Table 3 (protocol Section 9.5.4.3) the actual value and the change from baseline to each postbaseline visit and to the end of treatment (defined as the last on treatment value) will be summarized by visit using descriptive statistics. Qualitative parameters listed in Table 3 (protocol Section 9.5.4.3) will be summarized using frequencies (number and percentage of subjects), and changes from baseline to each postbaseline visit and to end of treatment will be reported using shift tables. Percentages will be based on the number of subjects with both nonmissing baseline and relevant postbaseline results.

6.7.3.1 Hematology and Clinical Chemistry

Laboratory parameters that are graded in CTCAE v5.0 will be summarized by CTCAE grade. In the summary of laboratory parameters by CTCAE grade, for parameters with CTCAE grading in both high and low direction, CTCAE in high and low directions will be summarized separately. Subjects with treatment-emergent markedly abnormal laboratory

values (TEMAV) will also be summarized. Markedly abnormal is defined as a value that is above or below the normal range and the CTCAE grade increased from baseline by 2 or more grades.

Laboratory test results will be reported in the following methods: hematology and blood chemistry.

- Summary of values at each visit and changes from baseline.
- Shifts from baseline to the worst postbaseline CTCAE grade.
- Summary of Treatment-emergent markedly abnormal laboratory results by cycle

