**Table 3 Clinical Laboratory Tests**

Category	Parameters
Hematology	Hematocrit, hemoglobin, platelets, RBC count, WBC count with differential (bands, basophils, eosinophils, lymphocytes, monocytes, neutrophils), and ANC
Chemistry	
Screening/Baseline/ End-of-Treatment Panel	Pregnancy test (serum $\beta$ -hCG), LDH, chloride, potassium, sodium, BUN, serum creatinine, phosphorus, calcium, albumin, total protein, alkaline phosphatase, ALT, AST, total bilirubin, CPK, TSH, and free T 4 in the case of abnormal TSH
Treatment Panel	Chloride, potassium, sodium, BUN, serum creatinine, phosphorus, calcium, albumin, total protein, alkaline phosphatase, ALT, AST, total bilirubin, CPK Serum TSH, free T 3 , and free T 4 , and in the case of abnormal TSH: anti-thyroglobulin antibodies and anti-thyroid peroxidase antibodies
Urinalysisa	Glucose, protein, leukocytes, nitrites, ketones, bilirubin, blood, urobilinogen, pH, and specific gravity. Microscopic examination of sediment to include: bacteria, casts, crystals, epithelial cells, RBCs, and WBCs Urine pregnancy test (Cycle 1 Day 1 only)

ALT = alanine aminotransferase, ANC = absolute neutrophil count, AST = aspartate aminotransferase,  $\beta$ -hCG = beta human chorionic gonadotropin, BUN = blood urea nitrogen, LDH = lactate dehydrogenase, RBC = red blood cell, T3 = triiodothyronine, T4 = thyroxine, TSH = thyroid-stimulating hormone, WBC = white blood cell, CPK = creatine phosphokinase.

a: When a local laboratory is required for a urinalysis, a Urinalysis Reagent Test Strip (URS-10) may be used.

Clinical laboratory tests will be performed by a central laboratory. All blood and urine samples will be collected and sent to the central laboratory on the day of collection unless otherwise instructed. In cases of a safety concern, blood samples will be split, or two samples drawn, to allow a local laboratory analysis in addition to the central laboratory.

All hematology, blood chemistry (including pregnancy test, as applicable), and urinalysis samples are to be obtained before study drug administration and results reviewed before administration/dispensing of study drug at the beginning of each treatment cycle. Refer to [Table 1](#) for dose interruption and reduction instructions in the event of clinically significant laboratory abnormalities.

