a: **Pretreatment:** Screening up to 28 days before start of treatment except for signing of the ICF which may be up to 8 weeks before the first dose of study drug; Baseline up to 7 days before start of treatment. If Screening laboratory tests (Hematology, Chemistry, and serum pregnancy) are performed within 7 days prior to Cycle 1 Day 1, these tests may count as Baseline tests and need not be repeated at Baseline. If Baseline central laboratory test results are not available in time to confirm eligibility, the local site laboratory results (including from Cycle 1 Day 1) may be used for this purpose.

**Treatment:** cycles of 21 days, up to 8 cycles; applicable to the Lead-in only, if subject is treated beyond Cycle 8 per protocol, the same assessments should be performed as for Cycles 1 to 8; however, no PK samples will be collected after Cycle 8.

**Extension:** Up to 3 years.

**Day 8 Assessments:** Day 8 assessments are required in cycles 1-3, and are optional on cycle 4 and beyond.

**EOT:** Tumor assessments are only required at EOT if they affect GRS. Other EOT tests (with the exception of serum pregnancy test, and QoL) need only be performed if the EOT visit is > 7 days from the most recent Cycle Day 1 visit.

- b: A biopsy sample will be sent to a central laboratory for testing of CD25 expression by IHC. The sample may be sent in formalin, or may be a formalin fixed paraffin embedded (FFPE) sample block, or may be sent as slides (minimum of five slides). Results must be obtained before enrollment of subject in the study. Results obtained at Screening or from an archival tumor biopsy ( $\leq 6$  months) can be used as long as the test was performed by the study-designated central laboratory. Multiple lesions may be tested. Re-biopsy with selection of the most representative lesion is required if the subject had disease progression or relapse since the last biopsy, or had received anticancer therapy since the last biopsy.
- c: Blood sampling, if blood assessment required for CTCL diagnosis; whole blood to be collected for flow cytometry analysis by central laboratory. Lymph node biopsy (if required per [Olsen 2011](#)): allow either fine needle aspirate or core biopsy; if additional lymph node analysis is required, surgical biopsy may follow, if required for CTCL diagnosis and/or staging; lymph node analysis to be performed by local site laboratory.

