- h: Chemistry laboratory tests should include the following thyroid function tests: serum TSH, free T3, free T4, and if these are abnormal, then include anti-thyroglobulin antibodies and anti-thyroid peroxidase antibodies (reflex testing at central laboratory only). Laboratory tests should also include serum  $\beta$ -hCG and LDH (screening only), chloride, potassium, sodium, BUN, serum creatinine, phosphorus, calcium, albumin, total protein, alkaline phosphatase, ALT, AST, total bilirubin, and CPK. Hematology laboratory tests include hematocrit, hemoglobin, platelets, RBC count, WBC count with differential (bands, basophils, eosinophils, lymphocytes, monocytes, neutrophils), and ANC. If Screening laboratory tests (Hematology, Chemistry, and serum pregnancy) are performed within 7 days prior to Cycle 1 Day 1, these tests may count as Baseline tests and need not be repeated at Baseline. On Day 1 of each cycle, laboratory assessments (local site laboratory) must be reviewed prior to drug administration, in addition to submitting to the central lab. For Cycle Day 8, a window of  $\pm 1$  day is allowed.

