#### **TREATMENT PHASE AND EXTENSION PHASE ASSESSMENT SCHEDULES**

##### **Treatment Period:**

Refer to the Schedule of Assessments, [Table 4](#), for a description and the schedule for all cycle day and EOT assessments.

Day 8 assessments are required during Cycles 1-3 and are optional on Cycle 4 and beyond.

EOT: Tumor assessments are only required at EOT if they affect GRS. Other EOT tests (with the exception of serum pregnancy test, and QoL) need only be performed if the EOT visit is > 7 days from the most recent Cycle Day 1 visit.

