### **LABORATORY VALUES**

Clinical laboratory values will be evaluated for each laboratory parameter by subject. Abnormal laboratory values will be identified as those outside (above or below) the normal range. Reference (normal) ranges for laboratory parameters will be included in the clinical study report for this protocol. Descriptive summary statistics for laboratory parameters and their changes from baseline will be calculated.

Laboratory parameters that are graded in CTCAE v5.0 will be summarized by CTCAE grade.

Clinical laboratory results postbaseline will be evaluated for markedly abnormal values. The National Cancer Institute's CTCAE v5.0 will be used to identify subjects with markedly abnormal laboratory values. The incidence of markedly abnormal values will be summarized by cycle. For the incidence of markedly abnormal laboratory values, each subject may be counted once in the laboratory parameter value high category and once in the laboratory parameter low category, as applicable.

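### Markedly abnormal laboratory results are tabulated by cycle, but Day 8 sampling is required only in Cycles 1 to 3, so rates before and from Cycle 4 are not comparable

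*SAP*

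**What the plan says.** SAP 6.7.3.1 lists among the laboratory displays a "Summary of Treatment-emergent markedly abnormal laboratory results by cycle". A value counts as markedly abnormal if it lies outside the normal range and "the CTCAE grade increased from baseline by 2 or more grades". Protocol 9.7.1.9 (Laboratory Values) makes the same commitment: "The incidence of markedly abnormal values will be summarized by cycle".

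The sampling schedule is in protocol 9.5.5.1. Table 4 marks hematology and chemistry on Day 1 and, conditionally, on Day 8. Footnote h, which covers these tests, sets a Day 8 window ("For Cycle Day 8, a window of" one day either side). Footnote a states that "Day 8 assessments are required in cycles 1-3, and are optional on cycle 4 and beyond", and protocol 9.5.5.2 repeats it: "Day 8 assessments are required during Cycles 1-3 and are optional on Cycle 4 and beyond". The text under Table 3 in protocol 9.5.4.3 requires that "All hematology, blood chemistry (including pregnancy test, as applicable), and urinalysis samples are to be obtained before study drug administration" at the start of each cycle, so Day 1 values are pre-dose.

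SAP Section 9 takes as baseline the last non-missing value before first dose. It admits unscheduled visits to worst-postbaseline analyses and leaves them out of by-visit analyses, but does not mention the by-cycle table. SAP 6.7.3 bases percentages on subjects with a baseline and a relevant postbaseline result. Neither document restricts the by-cycle table to a common visit or sets a Day 8 denominator for it.

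**The concern.** E7777 is given on Days 1 to 5 of a 21-day cycle. On the planned schedule Day 8 falls 3 days after the last infusion and the next Day 1 falls 17 days after it, or later if the cycle is delayed. The two visits therefore look at different parts of the cycle, and the table combines them in proportions that change at Cycle 4. A subject in Cycle 5 with only a pre-dose Day 1 sample can count as evaluable, although no sample was taken after that cycle's dosing.

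What is at stake is how the table is read. A lower rate from Cycle 4 could be taken to mean that laboratory toxicity eases with continued treatment. That reading comes easily here: protocol 7.3.1 reports that exposure to ONTAK fell by 75% between Cycles 1 and 3. Premedication also becomes optional at Cycle 4 (protocol 9.4.1.1), so the same boundary could be used to judge later-cycle tolerability. As planned, the table cannot separate a change in risk from a change in sampling.

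**Working it through.** The plan gives no rate for this table, so there is no figure to reproduce. The check has two steps.

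**Step 1. Required post-baseline samples per cycle** (protocol Table 4 with footnotes a and h, protocol 9.5.4.3, SAP Section 9)

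| Cycle | Required post-baseline samples | Of these, after that cycle's dosing |
|---|---|---|
| 1 | Day 8 (a pre-dose Day 1 value is baseline) | 1 |
| 2 and 3 | pre-dose Day 1, Day 8 | 1 |
| 4 onward | pre-dose Day 1 | 0 |

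An end-of-treatment sample can add one value in the last cycle only, and only if that visit is more than 7 days after the latest Day 1. The table labels each Day 1 value with the cycle it opens, which the SAP does not state. If Day 1 were credited to the preceding cycle instead, Cycles 1 to 3 would have two required samples each and later cycles one, so the step at Cycle 4 would remain.

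**Step 2. Expected rate under constant risk**

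Let d8 and d1 be the probabilities of a markedly abnormal value on Day 8 and on pre-dose Day 1, and u the share of subjects with the optional Day 8 sample from Cycle 4. None of the three is in the documents, so all are assumptions. Treat the two days as independent and optional sampling as random.

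- Cycle 1: d8
- Cycles 2 and 3: 1 − (1 − d8)(1 − d1)
- Cycle 4 onward: u × [1 − (1 − d8)(1 − d1)] + (1 − u) × d1

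With d8 = 20% and d1 = 5%, Cycle 1 is 20% and Cycles 2 and 3 are 1 − 0.80 × 0.95 = 24.0%. At u = 0.5, Cycle 4 onward is 0.5 × 24.0% + 0.5 × 5% = 14.5%.

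| u | Cycle 4 onward | Relative fall from Cycles 2 and 3 |
|---|---|---|
| 0 | 5.0% | 79% |
| 0.25 | 9.8% | 59% |
| 0.50 | 14.5% | 40% |
| 0.75 | 19.3% | 20% |
| 1 | 24.0% | 0% |

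Other assumed risks:

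| d8, d1 | Cycles 2 and 3 | Cycle 4 onward, u = 0 | Cycle 4 onward, u = 0.5 |
|---|---|---|---|
| 20%, 10% | 28.0% | 10.0% (64% fall) | 19.0% (32% fall) |
| 20%, 2% | 21.6% | 2.0% (91% fall) | 11.8% (45% fall) |
| 10%, 0% | 10.0% | 0% (100% fall) | 5.0% (50% fall) |
| 20%, 20%, same subjects (full persistence) | 20.0% | 20.0% (no fall) | 20.0% (no fall) |

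Independence matters little. If every subject abnormal on Day 1 were also abnormal on Day 8, the 20%/5% case would give 20% in Cycles 2 and 3, and the fall at zero uptake would be 1 − 5/20 = 75% instead of 79%.

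With the visits separated, the same inputs give 5% at every Day 1 from Cycle 2 and 20% at every Day 8 among those sampled. The artefact is then zero, provided optional Day 8 samples are not taken selectively.

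**The case against.** Day 8 is made optional, not withdrawn. At full uptake there is no fall, and there is none if abnormalities last until the next Day 1. The risks above are assumptions, and the gap between Day 8 and Day 1 risk drives the result. This stands: the documents support a direction under constant risk, not a size.

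Nor are Day 1 values always recovered values. Protocol Table 1 excepts Grade 3 lymphopenia and Grade 3 liver enzyme elevation from the relevant interruption rules, and protocol 9.4.1.3 calls for CPK testing whenever capillary leak syndrome is suspected, so some post-dose values will exist in later cycles. This also stands, and it narrows the effect for those parameters.

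Other displays help. The by-visit summaries in SAP 6.7.3.1 report Day 1 and Day 8 separately, and the shift to worst postbaseline grade makes no comparison between cycles. Neither is affected. But the by-visit summaries describe values and changes, while the incidence of markedly abnormal results is planned by cycle. SAP Sections 10 and 12 defer derivations and table shells to separate documents that may settle the matter; the SAP itself does not.

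A reader might go further and infer that the rate must fall from Cycle 4 by construction, or fall sharply. The documents do not support this, because they give neither uptake nor persistence. A reader might also infer that selective Day 8 testing could push the later overall rate in either direction. Under constant risk, and with a Day 1 sample in every subject, it cannot lift that rate above the one in Cycles 2 and 3, since it only restores part of the missing information. Selection can inflate a rate calculated among Day 8 samples alone, which is a separate point and needs a footnote.

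**Conclusion.** The concern holds as a comparability problem in one table. Required sampling changes at Cycle 4, the by-cycle table ignores this, and under constant risk the expected later rate is biased downward whenever some subjects skip Day 8 and some abnormalities resolve before the next Day 1. In the 20%/5% illustration the relative fall runs from 79% at zero uptake to none at full uptake. Across the other assumed risks at zero uptake it runs from none, with full persistence, to 100%.

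The consequence is limited. The table is descriptive, in a single-arm study, with no test or decision rule attached. Subjects who stop early also leave the later cycles, which is a separate influence on any trend. The harm lies only in reading the table as a course over time.

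**What to change.** In SAP 6.7.3.1 and the matching table shell:

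- Keep the by-cycle table, which the protocol commits to, and split it by visit type: pre-dose Day 1 from Cycle 2 onward, noted as reflecting the preceding cycle's dosing, and Day 8 in all cycles.
- Use the number of subjects sampled at that visit as the denominator, so that Day 8 uptake in each cycle is visible.
- State how end-of-treatment and unscheduled values are assigned to cycles.
- Add a footnote that overall rates in Cycles 1 to 3 and from Cycle 4 are not comparable, and that Day 8 results from Cycle 4 may come from selected subjects.

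The cost is some SAP wording and a longer table or one extra shell. No new data are needed. Because the by-cycle table stays and optional Day 8 results remain in it, the protocol's commitment is still met.

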6.7.3.2 Urinalysis

A listing of urinalysis results will be provided.

6.7.4 Vital Signs

Descriptive statistics for vital signs parameters (systolic and diastolic blood pressure (BP), heart rate, respiratory rate, body temperature and weight) and their change from baseline value will be presented by visit.

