#### 9.4.1.4 Management of Acute Infusion Reaction and Hypersensitivity During Administration

The administration of E7777 should be withheld if the subject develops any of the following:

- Diastolic pressure below 60 mmHg or above 100 mmHg
- Pulse rate faster than 130 beats per minute (bpm)
- Shaking chills, rigors
- Oral temperature higher than 39.4 °C

- Respiratory distress

Administration of E7777 can be resumed if the subject's signs and symptoms return to baseline; E7777 administration will be withheld for that day if the condition does not resolve.

In the event a hypersensitivity reaction occurs, the following medications should be readily available during each administration:

- Diphenhydramine (50-mg i.v. push) or other antihistamine per local institutional guideline for hives, itching, rash, shortness of breath, and/or chills
- Methylprednisolone sodium succinate (250-mg/mL i.v. push) or per local institutional guideline for decrease in blood pressure (BP) and/or respiratory distress
- Epinephrine 0.1 to 0.5 mL of a 1:1000 solution subcutaneous for anaphylaxis
- Prochlorperazine (10-mg i.v. push) or institutional antiemetic agent of choice. Subjects may receive antiemetics, as needed, for the control of nausea and/or vomiting

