#### 9.5.4.4 Vital Signs

Vital sign measurements (i.e., systolic and diastolic BP [mmHg], pulse [bpm], respiratory rate [per minute], body temperature [in degrees centigrade]), will be measured as signals for potential vascular leak syndrome. Measurements will be obtained before and at the end of the infusion and 30 minutes post-infusion on treatment days at the visits designated in the Schedule of Assessments (Table 4).

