- d: Concomitant medications to be reviewed at every visit, until 30 days after the last treatment dose. Use of topical or systemic steroids within 14 days of Cycle 1 Day 1 is not allowed, with the exception noted under “Concomitant Medications” (see [Section 9.4.7](#)).
- e: Vital signs measured at baseline and EOT (if necessary), and on drug treatment days and on Cycle Day 8 ( $\pm 1$  day), before and at the end of the infusion and 30 minutes after infusion. A complete physical examination will be performed at Baseline, Day 1 of each cycle, and at Study Termination (discontinuation from study). A symptom-directed examination will be performed on all other visit days. All physical examinations are to include monitoring of weight and blood pressure as signals for potential vascular leak syndrome.
- f: Single 12-lead ECGs will be performed during Screening, on Day 1 of each cycle and at End of Treatment.
- g: On Cycle Day 1 (i.e. treatment day), urinalysis will be performed prior to study drug administration. Urinalysis includes glucose, protein, leukocytes, nitrites, ketones, bilirubin, blood, urobilinogen, pH, and specific gravity. Microscopic examination of sediment includes bacteria, casts, crystals, epithelial cells, RBCs, and WBCs. When a local laboratory is required for a urinalysis, a Urinalysis Reagent Test Strip (URS-10) may be used. On Cycle 1 Day 1 only: a urine pregnancy test will be performed prior to study drug administration.

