### **VITAL SIGNS**

Descriptive statistics for vital signs parameters (i.e., sitting diastolic and systolic BP, sitting pulse rate, respiratory rate, temperature, weight, and changes from baseline) will be presented by visit.

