4.2 Overall Study Design and Plan

This is a multicenter open-label, single-arm study of E7777 in subjects with recurrent or persistent CTCL.

A sufficient number of subjects in the Main Study will be recruited so that approximately 70 Stage I – III subjects from both the Main Study and the Lead-In Study in the 9 µg/kg/day dose group with recurrent or persistent CTCL are treated with E7777 to assess efficacy. Safety will be evaluated in all subjects from the Main Study, and in Lead-In subjects from the 9µg/kg/day dose group. The dose of E7777 in the Main Study is selected from results of the Lead-In part of the study. The primary efficacy analysis will be based on Stage I – III subjects treated at 9 µg/kg/day, which includes subjects from both the Main Study plus the Lead-In.

Study Phases for Each Subject

Subjects in the study will move through three phases while on study.

- **Pretreatment Phase** includes a Screening Period and a Baseline Period:
 - **Screening Period** is from Day -28 to the start of treatment (Cycle 1 Day 1) except for signing of the informed consent form (ICF) which may have been up to 8 weeks before the first dose of study drug. The purpose of the Screening Period is to obtain informed consent and to ensure that each subject met all the specified eligibility criteria.
 - **Baseline Period** is from Day -7 to the start of treatment. Subjects who completed the Baseline assessments and met the eligibility criteria began treatment in the Treatment Phase.
- **Treatment Phase** consists of the following periods:
 - **Treatment Period.** E7777 will be administered by intravenous (IV) infusion over 60 minutes (± 10 minutes) on 5 consecutive days every cycle of 21 days. Treatment with E7777 for up to 8 cycles; each cycle of 21 days is one Period. Subjects who attained skin tumor response and derived clinical benefit from E7777 treatment could continue receiving treatment beyond 8 cycles, at the discretion of the treating physician.
 - **Follow-Up Period.** Tumor assessment until discontinuation of treatment due to progressive disease (PD); immunogenicity, and survival follow-up until relapse or initiation of new systemic anti-cancer therapy. All Follow-up assessments will be performed for up to 3 years after end of treatment, or until sponsor termination of the study.

After data cutoff for the primary analysis in the Main Study, the study moved to the Extension Phase.

- **Extension Phase** consists of the following periods:

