9 DEFINITIONS AND CONVENTIONS FOR DATA HANDLING

Baseline

Baseline is defined as the non-missing value most recently collected before the first dose of any study.

In the analyses of ORR and CBR, subjects without baseline or postbaseline tumor assessment will be considered as non-responders and will be included in the denominator when calculating ORR and CBR. Non-responders will be excluded in the analysis of DOR.

Study Day 1

Study Day 1 is defined as the day of the first dose of study drug administered.

By-visit analysis

All by-visit analyses will be performed using assessment at corresponding scheduled visits recorded in the eCRF (not including unscheduled).

The unscheduled visits will be included in the analyses that involve definition of worst post-baseline assessment.

Time Conversion Factors

The following factors will be used to convert days to months or years:

1 month = 30.4375 days; 1 year = 365.25 days.

Missing/Partial Dates

Refer to programming specifications for details to handle any missing or partial dates.

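### Vital signs are summarised only by scheduled visit, so the number of subjects with a marked blood pressure, pulse or temperature excursion cannot be read from the vital-sign tables

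*SAP*

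**What the plan says.** **Why the data are collected.** Protocol 9.5.4.4 says vital signs "will be measured as signals for potential vascular leak syndrome". Readings are taken "before and at the end of the infusion and 30 minutes post-infusion on treatment days", and dosing is "on 5 consecutive days every cycle of 21 days" (SAP 4.2). Footnote e of the protocol's schedule of assessments adds: "All physical examinations are to include monitoring of weight and blood pressure as signals for potential vascular leak syndrome". Protocol 9.4.1.3 also asks for body weight before each infusion.

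**How they are analysed.** SAP 6.7.4 plans descriptive statistics for systolic and diastolic pressure, heart rate, respiratory rate, temperature and weight, and "their change from baseline value will be presented by visit". Protocol 9.7.1.9 has the same plan: "temperature, weight, and changes from baseline) will be presented by visit". SAP sections 6 and 6.7 define the statistics as mean, SD, median, quartiles, minimum and maximum. SAP 6.7.6 plans no further safety analysis.

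**Unscheduled data.** SAP section 9 states: "All by-visit analyses will be performed using assessment at corresponding scheduled visits recorded in the eCRF (not including unscheduled"). The next sentence there admits unscheduled visits only to analyses that use a worst post-baseline assessment. Vital signs have none.

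**Other safety data.** SAP 6.7.3.1 gives laboratory results a shift to worst grade and a summary of markedly abnormal values. SAP 6.7.5 gives ECG a shift to worst value and counts of subjects above QTcF limits.

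**The concern.** Leak and infusion reactions occur in individual subjects on particular days. The natural safety question is how many subjects ever had a marked excursion, and in which cycle. A by-visit table describes the distribution across subjects at one visit and does not link a subject's visits. Vital signs, which the protocol ties to a named toxicity, therefore get a weaker summary than laboratory or ECG data.

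The adverse event tables fill the gap only in part. Protocol 9.5.4.1 gives explicit rules for when a laboratory value or a QTc result becomes an adverse event, but no numeric rule for blood pressure or weight. Hypotension enters those tables when an investigator reports it. SAP 6.7.2.1 leaves the events of special interest to be identified from later data review.

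There is also a gap in specification. Each dosing day has three scheduled readings, and SAP 6.7.4 does not say which one represents the visit.

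**Working it through.** The documents give no hypotension incidence, no SD for blood pressure change and no figure for vital signs to reproduce. Incidence, size of fall and SD below are assumptions. The 70 subjects, five dosing days per cycle and three readings per day come from the documents.

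**1. What the mean shows.** If a proportion p of subjects each have one fall of size d, spread evenly over V visits, the mean at each visit moves by p × d / V. With p = 0.25 and d = 30 mmHg:

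| Spread over | Shift in by-visit mean |
|---|---|
| 1 visit | 0.25 × 30 / 1 = 7.5 mmHg |
| 5 visits (one cycle) | 0.25 × 30 / 5 = 1.5 mmHg |
| 15 visits (Cycles 1 to 3) | 0.25 × 30 / 15 = 0.5 mmHg |

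The standard error of a visit mean with 70 subjects is 10/√70 = 1.2 mmHg for an SD of 10, and 15/√70 = 1.8 mmHg for an SD of 15. The shift is below one standard error over 15 visits, close to one over 5 (1.5/1.8 = 0.8 to 1.5/1.2 = 1.3), and about 4 to 6 at a single visit (7.5/1.8 to 7.5/1.2). Whether the mean shows the effect depends on clustering in time.

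**2. What the minimum shows.** Simulated for 70 subjects with Normal changes, SD 10 and 25% of subjects having one 40 mmHg fall over 8 visits (600 replicates), the lowest minimum in the table averages about −58 mmHg, against −31 with no events. With SD 15 and 40 visits it is −67 against −53. A severe fall at a scheduled reading does leave a trace.

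**3. Whether the count can be recovered.** Suppose a visit's minimum is beyond a limit and its first quartile is within it. Those two columns alone allow anything from 1 to 17 of 70 subjects (1/70 = 1.4% to 17/70 = 24%) beyond the limit at that visit. If two visits look like this, the number of different subjects is between 1 and 2 × 17 = 34, because the table does not say whether the low values belong to the same people. With five such visits, 5 × 17 = 85 exceeds 70, so any number from 1 to 70 is possible. The mean and SD narrow this at a single visit but do not link subjects across visits.

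**4. What a worst-value table would show.** It counts subjects, but adds background. Cycles 1 to 3 give 15 × 3 = 45 readings per subject. If changes were independent and Normal, the chance that a subject with no event has at least one fall of 30 mmHg or more is:
- SD 15: 1 − (1 − 0.0228)^45 = about 65%
- SD 10: 1 − (1 − 0.00135)^45 = about 6%

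Readings within a subject are correlated, so these figures only show how strongly the background depends on SD and on the limit chosen.

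**The case against.** The strongest counter-argument is that the harm is already covered elsewhere. CLS needs at least two of hypotension, edema or low albumin (Protocol 9.1.2). Albumin gets worst-grade tables. Reported CLS, hypotension and infusion reactions are tabulated by worst grade, with listings and tables of events leading to interruption or discontinuation. Protocol and SAP agree on the by-visit plan, and table shells not available here may separate the infusion time points. Most of this stands, and it limits the point to the vital-sign tables. It does not supply a count from the measured data.

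Four stronger readings are tempting, and the documents do not support them:
- **That only mean change is reported.** Actual values, median, quartiles, minimum and maximum are also planned.
- **That frequent hypotension would be nearly invisible.** This holds for the mean and quartiles only if falls are spread over many visits. Clustering at one visit moves the mean by 7.5 mmHg in the illustration, and the minimum can reveal a severe scheduled fall in either case.
- **That readings taken during a reaction are discarded.** SAP section 9 speaks of unscheduled visits. The end-of-infusion and 30-minute readings are scheduled. The documents do not say whether extra readings on a dosing day are captured or excluded.
- **That a worst-value table would show the true incidence directly.** Step 4 shows that it would not.

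**Conclusion.** The point holds in limited form. Blood pressure, pulse and temperature are collected repeatedly on every dosing day as leak signals, yet no planned vital-sign table counts the subjects with a marked excursion, and unscheduled visits enter none of them. An assumed 25% incidence (0.25 × 70 = 17.5, or about 17 to 18 subjects) could not be read from the tables, although individual extreme values might be seen. The 0.5 to 7.5 mmHg range rests on the assumed 25%, 30 mmHg and timing, none of which comes from the documents. This is an inexpensive improvement to a descriptive safety analysis. It does not affect the primary result, and it is not a contradiction between protocol and SAP.

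**What to change.** Add to SAP 6.7.4, for the Safety Analysis Set and the Stage I-III Safety Analysis Set:

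1. A subject-level worst post-baseline table using all on-treatment readings, scheduled and unscheduled. Give the number and percentage of subjects beyond pre-specified reporting limits, by cycle and overall. Show baseline status in shift format, so that subjects already beyond a limit are kept.
2. Limits set by the sponsor's clinical team as reporting cut-offs only. Protocol 9.4.1.4 is one available source (for example "Diastolic pressure below 60 mmHg or above 100 mmHg", with pulse and temperature values in the same list), but it has no systolic or weight limit. Nothing in this changes treatment rules.
3. Each subject's largest fall in systolic pressure from the pre-dose value on Day 1 of the same cycle, with median, quartiles and extremes.
4. A statement of which of the three same-day readings the by-visit table uses, or the three shown separately.
5. Within-cycle weight gain only if the pre-infusion weights are in the database. Protocol 9.5.4.5 specifies weight at baseline, Day 1 of each cycle and termination, and the documents do not say that the daily weights are on the CRF. Otherwise use change from Day 1 to Day 1.

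**Cost.** SAP wording and a little programming; the blood pressure, pulse and temperature readings are already scheduled. The real downside is interpretation. Many readings per subject, more of them in symptomatic subjects and no control arm will inflate worst-value percentages. The SAP should say that the table is descriptive and read alongside the adverse event data.
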